5.3. Medical History

Medical history documentation will include all medical conditions, surgeries, or drug allergies within the prior year. Also, any clinically significant abnormalities found during the Screening physical exam should be documented as medical history. Medical history will be coded using the MedDRA version 23.1 or higher. The number and percentage of participants with any medical history will be summarized by treatment arm using SOC and PT, with SOCs and PTs within each SOC sorted in descending order of frequency in the ADG20 arm. Percentages will be calculated based on number of participants in each treatment group in the FAS and the mFAS-non-Omicron. If the same medical history (based on PT) is reported for the same participant more than once, the medical history is counted only once for the PT.

Participant medical history data including specific details will be presented in a listing.

5.4. Treatments and Medications

5.4.1. Prior and Concomitant Medication

A prior medication is defined as any medication that is taken within 30 days prior to dosing of study drug. A concomitant medication is defined as any medication that has a stop date that is on or after the date of study drug dosing or is ongoing after dosing.

All medications used within 30 days prior to the date of randomization up to and including Day 60 will be collected on the CRF. In addition, any concomitant medications related to AEs and any vaccinations received will be recorded for the entire length of the study (ie, through Month 14). All medications will be coded according to the World Health Organization drug dictionary (WHODrug March 2021) or higher.

The number and percentages of participants with at least one prior/concomitant medication will be summarized by treatment group. The number and percentages of all prior/concomitant medications will be summarized by treatment group, WHODrug ATC level 2 and PT. All summaries will be performed using the FAS. A listing of prior/concomitant medications by participant will be provided.

The number and percentages of participants with at least one prohibited concomitant medication (refer to ADG20-TRMT-001 Designated Background Standard of Care document) for the treatment of COVID-19 or receiving a COVID-19 vaccine will be summarized by treatment group in the FAS and the mFAS-non-Omicron. The number and percentages of these medications will also be summarized by treatment group, WHODrug ATC level 2 and PT, and a listing of prohibited medications by participant will be provided.

Medications with missing dates will follow the imputation rules in [Appendix C](#) to categorize as prior, concomitant, or prohibited up through Day 29. Medications are sorted by decreasing frequency of ATC Level 2 in the ADG20 arm, then by decreasing frequency of PT in the ADG20 arm.

5.4.1.1. Concomitant Procedures

A listing of concomitant procedures as collected on the eCRFs will be provided.

5.4.1.2. Study Treatments

A single 300 mg dose of ADG20 or matching placebo will be administered by IM injection. Summaries of study treatment will be presented for the Safety Set. The number and percentage of participants that received a full dose (300 mg) and did not receive a full dose will be presented. Descriptive statistics of the total volume (mL) and dose (mg) will be presented; mL is converted to mg as follows: $100 \times \text{dose in mL}$. A listing of study drug administration and of study drug exposure exceptions (study drug not administered, full dose not administered, and/or study drug not received as randomized) will be provided.

5.5. Efficacy Analyses

5.5.1. Primary Efficacy Analysis

The primary efficacy endpoint is the incidence of COVID-19-related hospitalization or all-cause death through Day 29 in the mFAS-non-Omicron analysis set. The null and alternative hypotheses are the following:

$$H_0: P_1 - P_0 = 0$$

$$H_1: P_1 - P_0 \neq 0$$

P_1 and P_0 are the proportion of participants with COVID-19-related hospitalization or all-cause death through Day 29 in the ADG20 and placebo groups respectively. Using the methodology as described below (with additional details in [Appendix J](#)), a standardized estimator for a binary outcome (standardized risk difference/standardized relative risk reduction) will be estimated with adjustment for the following prognostic factors: age (continuous), sex (categorical), baseline qualitative serostatus (categorical: positive, negative), BMI (continuous), and baseline viral load from NP sample (continuous as \log_{10} copies/mL). For all efficacy analysis models, missing baseline serostatus will be imputed as positive and missing baseline BMI and viral load will be imputed as the average of all participants with non-missing data at baseline. Age is a randomization stratification factor and, thus, cannot be missing.

[Appendix I](#) summarizes the main estimation and sensitivity analyses for the primary estimand (Estimand 1a). The main estimation for Estimand 1a will use available data for COVID-19 hospitalization or all-cause death through Day 29, implemented in the mFAS-non-Omicron analysis set. Missing status on COVID-19-related hospitalization or all-cause death will be imputed as not having a COVID-19 hospitalization or all-cause death. The number and percentages of participants who experience and do not experience a COVID-19-related hospitalization or all-cause death will be summarized by treatment group, including summaries of missing data, COVID-19-related hospitalizations, and all-cause death. The observed risk difference (placebo minus ADG20) with 95% CI (using the Miettinen-Nurminen method), observed relative risk reduction, standardized risk difference with 95% CI and associated p-values, and standardized relative risk reduction with 95% CI will be provided.

The method described in [Ge et al. \(2011\)](#) computes a population-level estimate for the treatment difference (in terms of difference in proportion) and supports an adjustment for the pre-defined prognostic factors. The method relies on a logistic regression model that includes COVID-19-related hospitalization or all-cause death present or absent as the dependent variable and treatment and prognostic factors as independent variables. To define this model, consider the i th participant, $i = 1, \dots, n$, where n is the total number of participants, and let y_i denote the binary outcome for the primary endpoint (COVID-19-related hospitalization or all-cause death, present=1 or absent=0). The treatment indicator will be denoted by t_i , where $t_i = 0$ corresponds to the placebo arm and $t_i = 1$ corresponds to the treatment (ADG20) arm. The vector of prognostic factors for the i th participant will be denoted by \mathbf{x}_i . The model is given by:

$$\text{logit } p_i = \beta_0 + \beta_1 t_i + \boldsymbol{\beta}_2' \mathbf{x}_i,$$

where $p_i = P(y_i = 1)$, β_0 and β_1 are the intercept and slope, $\boldsymbol{\beta}_2$ is the vector of model parameters corresponding to the prognostic factors and the prime denotes transposition.

After the model has been fitted to the data, the model parameters will be estimated (the estimates will be denoted by $\hat{\beta}_0$, $\hat{\beta}_1$ and $\hat{\boldsymbol{\beta}}_2$, respectively). After that, two potential outcomes will be computed from the model for each participant. These outcomes represent the participant's outcomes if the participant has been assigned to the placebo and treatment arms:

$$p_{i0} = P(y_i = 1 | t_i = 0),$$

$$p_{i1} = P(y_i = 1 | t_i = 1).$$

The population-level estimates for the for the incidence rates will be defined as follows:

$$\hat{p}_0 = n^{-1} \sum_{i=1}^n p_{i0} \text{ and } \hat{p}_1 = n^{-1} \sum_{i=1}^n p_{i1}.$$

These estimates can be used to define an estimate for the treatment difference (difference in the incidence rates) or relative risk reduction in a straightforward manner, i.e.,

$$\hat{p}_1 - \hat{p}_0 \text{ and } 1 - \hat{p}_1/\hat{p}_0$$

The variance of the estimated treatment difference or relative risk reduction will be estimated using the delta method based on the algorithm presented in [Ge et al. 2011 \(Appendix J\)](#).

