5.5.2. Supplemental Estimand Analyses

[Appendix I](#) provides an overview of the main estimation and sensitivity analyses for the supplementary estimand (Estimand 1b). Estimand 1b utilizes a hypothetical strategy for the intercurrent event of receipt of prohibited treatments (refer to ADG20-TRMT-001 Designated Background Standard of Care document) for COVID-19 (IcEV3).

For participants with IcEv3, if the participant has not had a COVID-19-related hospitalization or death prior to the intercurrent event, the primary endpoint will be set to missing. Missing data for the supplementary analysis will be carried out using an MI based strategy that includes the following three steps:

- Step 1. Missing outcomes will be imputed multiple times ($M=100$) based on the intercurrent event handling strategy
- Step 2. The logistic regression analysis model presented above will be applied to each completed data set with terms including the prognostic factors and treatment variable and estimates of the treatment effect and associated standard error will be computed.
- Step 3. The individual completed sets will be combined using Rubin's rules to produce a single inferential statement (treatment effect, standard error, and p-value) via PROC MIANALYZE.

The imputation model will be informed by the observed outcomes from participants who either did not experience the intercurrent event or met the primary endpoint prior to receiving prohibited medication. The imputation model will include the prognostic factors as listed in Section [5.5.1](#). Further variables will be considered for inclusion in the MI model on the basis they may inform missingness or be correlated with the endpoint.

The final analysis model applied to the complete data set will be the same as that for the primary analysis.

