APPENDIX H. PRIMARY AND KEY SECONDARY OBJECTIVES AND ESTIMANDS

Objective	Primary: To evaluate the efficacy of ADG20 compared to placebo in the treatment of mild or moderate COVID-19 in participants at high risk of disease progression	Primary: To evaluate the efficacy of ADG20 compared to placebo in the treatment of mild or moderate COVID-19 in participants at high risk of disease progression	Key Secondary: To evaluate the effect of ADG20 on the following clinical parameters in participants with mild or moderate COVID-19 and high risk of disease progression	Key Secondary: To evaluate the effect of ADG20 on the following clinical parameters in participants with mild or moderate COVID-19 and high risk of disease progression
Estimand Label	Estimand 1a (Primary)	Estimand 1b (Supplementary to Primary)	Estimand 2 (Key Secondary 1)	Estimand 3 (Key Secondary 2)
Estimand Description (with Endpoint)	Treatment difference (ADG20 – Placebo) in proportion of COVID-19-related hospitalization or all-cause death through Day 29 regardless of co-infection with respiratory pathogens other than SARS-CoV-2, use of prohibited COVID-19 vaccine, or prohibited treatments for COVID-19	Treatment difference (ADG20 – Placebo) in proportion of COVID-19-related hospitalization or all-cause death through Day 29 regardless of co-infection with respiratory pathogens other than SARS-CoV-2 or use of COVID-19 vaccine and assuming no intake of prohibited treatments for COVID-19	Treatment difference (ADG20 – Placebo) in proportion of participants experiencing severe/critical COVID-19 or all-cause death through Day 29 regardless of co-infection with respiratory pathogens other than SARS-CoV-2, use of prohibited COVID-19 vaccine, or prohibited treatments for COVID-19	Treatment difference (ADG20 – Placebo) in proportion of participants experiencing COVID-19-related emergency room visits, hospitalization, or all-cause death through Day 29 regardless of co-infection with respiratory pathogens other than SARS-CoV-2, use of prohibited COVID-19 vaccine, or prohibited treatments for COVID-19
Target Population	Adult and adolescent participants with laboratory confirmed mild or moderate COVID-19 who are at high risk of disease progression	Same as Estimand 1a	Same as Estimand 1a	Same as Estimand 1a

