Endpoint	Incidence of COVID-19-related hospitalization or all-cause death through Day 29	Same as Estimand 1a	Incidence of severe/critical COVID-19 or all-cause death through Day 29	Incidence of COVID-19-related emergency room visits, hospitalizations, or all-cause death through Day 29
Treatment Conditions	IM ADG20, IM Placebo	Same as Estimand 1a	Same as Estimand 1a	Same as Estimand 1a
Population-Level Summary	Difference in proportion of COVID-19-related hospitalization or all-cause death through Day 29	Difference in proportion of COVID-19-related hospitalization or all-cause death through Day 29	Difference in proportion of severe/critical COVID-19 or all-cause death through Day 29	Difference in proportion of COVID-19-related emergency room visits, hospitalization, or all-cause death through Day 29

Objective	Primary: To evaluate the efficacy of ADG20 compared to placebo in the treatment of mild or moderate COVID-19 in participants at high risk of disease progression	Primary: To evaluate the efficacy of ADG20 compared to placebo in the treatment of mild or moderate COVID-19 in participants at high risk of disease progression	Key Secondary: To evaluate the effect of ADG20 on the following clinical parameters in participants with mild or moderate COVID-19 and high risk of disease progression	Key Secondary: To evaluate the effect of ADG20 on the following clinical parameters in participants with mild or moderate COVID-19 and high risk of disease progression
Estimand Label	Estimand 1a (Primary)	Estimand 1b (Supplementary to Primary)	Estimand 2 (Key Secondary 1)	Estimand 3 (Key Secondary 2)
IcEv1 (Co-Infection)	Treatment policy	Treatment policy	Treatment policy	Treatment policy
IcEv2 (Prohibited COVID-19 vaccine)	Treatment policy	Treatment policy	Treatment policy	Treatment policy
IcEv3 (Prohibited treatments for COVID-19)	Treatment policy	Hypothetical	Treatment policy	Treatment policy

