APPENDIX I. OVERVIEW OF STATISTICAL METHODS: ESTIMATIONS OF ESTIMANDS AND SENSITIVITY ANALYSES

Estimand Label	Estimand Description	Main Estimation			Sensitivity Analysis
		Analysis Set	Imputation/Data Handling Rules	Analysis Model/Method	
Estimand 1a	Treatment difference (ADG20 – Placebo) in proportion of COVID-19-related hospitalization or all-cause death through Day 29 regardless of intake of prohibited treatments for COVID-19	FAS	The endpoint will incorporate all available information through Day 29. Where participants have missing primary endpoint through Day 29, the status will be imputed as not having COVID-19-related hospitalization or all-cause death (ie, responder)	The endpoint will be analyzed using the methodology for determining a standardized estimator for a binary outcome, with adjustment for prognostic factors. The standard error of the standardized estimator will be estimated using the delta method (refer to Appendix K)	Multiple imputation under MAR assumption followed by calculation of standardized risk difference and 95% CI using Rubin's method. Control based imputation Per-protocol Set analysis
Estimand 1b	Treatment difference (ADG20 – Placebo) in proportion of COVID-19-related hospitalization or all-cause death through Day 29 assuming no intake of prohibited treatments for COVID-19	FAS	In case of prohibited treatments for COVID-19, the primary endpoint will utilize multiple imputation under MAR assumption. The imputation model will be informed by the observed outcomes from participants who did not receive such medication (or received it after meeting the primary endpoint). The logistic model will include the prognostic factors.	Same as Estimand 1a	Hypothetical strategy of handling the ICEs.
Estimand 2	Treatment difference (ADG20 – Placebo) in proportion of participants experiencing severe/critical COVID-19 or all-cause death through Day 29 in the target population	FAS	Same as Estimand 1a	Treatment difference in the proportion of participants with severe/critical COVID-19 or all-cause death through Day 29 will be presented and tested using the main analysis method outlined for Estimand 1a	

Estimand Label	Estimand Description	Main Estimation			Sensitivity Analysis
		Analysis Set	Imputation/Data Handling Rules	Analysis Model/Method	

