Estimand 3	Treatment difference (ADG20 – Placebo) in proportion of participants experiencing COVID-19-related emergency room visits, COVID-19-related hospitalization, or all-cause death through Day 29 in the target population	FAS	Same as Estimand 1a	Treatment difference in proportion of participants with COVID-19-related emergency room visits, COVID-19-related hospitalizations or all-cause death through Day 29 will be presented and tested using the main analysis method for Estimand 1a.	

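### SAP Appendix I gives FAS as the analysis set for Estimands 1a, 1b, 2 and 3; the body text gives mFAS-non-Omicron for 1a, 2 and 3 and names no set for 1b

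*SAP*

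**What the plan says.** SAP 5.5.1 introduces Appendix I as the summary of the main estimation and sensitivity analyses for Estimand 1a, and then states: "The main estimation for Estimand 1a will use available data for COVID-19 hospitalization or all-cause death through Day 29, implemented in the mFAS-non-Omicron analysis set".

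The Analysis Set column of Appendix I reads differently. In each row the first word below is the entry in that column:

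- Estimand 1a: "FAS The endpoint will incorporate all available information through Day 29"
- Estimand 1b: "FAS In case of prohibited treatments for COVID-19, the primary endpoint will utilize multiple imputation under MAR assumption"
- Estimand 2: "FAS Same as Estimand 1a Treatment difference in the proportion of participants with severe/critical COVID-19"
- Estimand 3: "FAS Same as Estimand 1a"

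SAP 5.5.3 places the binary key secondary endpoints (Estimands 2 and 3) in mFAS-non-Omicron. Protocol 7.6 and 7.7 use that set for the primary and key secondary analyses, and SAP 4.5.3 calls it the primary efficacy population.

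On the supplementary estimand, SAP 5.5.2 says "Estimand 1b utilizes a hypothetical strategy for the intercurrent event of receipt of prohibited treatments". It refers to Appendix I for the main estimation and names no analysis set of its own.

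Appendix H gives the target population of Estimand 1a as "Adult and adolescent participants with laboratory confirmed mild or moderate COVID-19 who are at high risk of disease progression", with no mention of variant. The other three estimands inherit that entry.

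**The concern.** FAS and mFAS-non-Omicron are different populations, not two names for one. SAP 4.5.2 defines FAS as everyone randomised, and SAP 4.5.3 restricts mFAS-non-Omicron to confirmed or suspected non-Omicron infection. Anyone programming from Appendix I would analyse the wrong population for the primary and both binary key secondary endpoints.

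For 1a, 2 and 3 the body text resolves the conflict. What is at stake there is a signed SAP that prints two populations for its primary estimand.

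Estimand 1b is less secure, because no body text names its set. A programmer could follow 5.5.1 for 1a and Appendix I for 1b, each as written. The two estimates would then differ in population as well as in how prohibited treatments are handled, and comparing them would not isolate the effect of those treatments. If both followed Appendix I they would share a set, but not the planned one.

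**Working it through.** **1. Where each set is named**

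| Estimand | Body text | Appendix I |
|---|---|---|
| 1a (primary) | mFAS-non-Omicron (SAP 5.5.1; protocol 7.6) | FAS |
| 1b (supplementary) | none named (SAP 5.5.2) | FAS |
| 2 (key secondary 1) | mFAS-non-Omicron (SAP 5.5.3; protocol 7.7) | FAS |
| 3 (key secondary 2) | mFAS-non-Omicron (SAP 5.5.3; protocol 7.7) | FAS |

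SAP 5.6 also repeats Estimands 1a, 2 and 3 in subgroups within mFAS-non-Omicron. The rule in SAP Section 1 that the SAP overrides the protocol does not help, because this conflict lies inside the SAP. SAP Section 7 reports no changes from the protocol's analyses, which does not fit FAS in Appendix I.

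**2. Which population the stated power belongs to**

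Inputs from SAP 4.2: about 320 participants, taken as 160 per arm; placebo risk 12%; relative reduction 70%; two-sided alpha 0.05.

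- ADG20 risk: 0.12 × 0.30 = 0.036. Risk difference (placebo minus ADG20): 0.12 − 0.036 = 0.084.
- Mean risk: (0.12 + 0.036)/2 = 0.078.
- Null SE: √(2 × 0.078 × 0.922 / 160) = 0.02998.
- Alternative SE: √((0.12 × 0.88 + 0.036 × 0.964) / 160) = 0.02961.
- Power: Φ((0.084 − 1.96 × 0.02998) / 0.02961) = Φ(0.852) = 0.803.

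This reproduces the plan's figure of about 80%, so that figure refers to mFAS-non-Omicron.

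**3. How many participants FAS would add**

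399 − 320 = 79, and 79/399 = 0.198. SAP 4.5.3 classes every participant without a sequence as suspected non-Omicron or suspected Omicron, so these 79 are the confirmed or suspected Omicron cases.

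**4. Effect on the tested quantity**

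Appendix H defines the population-level summary as "Difference in proportion of COVID-19-related hospitalization or all-cause death through Day 29", so the scale is the risk difference. Assume the 79 split equally by arm (39.5 each, 199.5 per arm in total), and let d be the risk difference among Omicron participants. Then

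FAS risk difference = (160 × 0.084 + 39.5 × d) / 199.5, which in points is 6.7 + 0.198 × d.

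| Assumption for Omicron participants | d (points) | FAS risk difference (points) |
|---|---|---|
| No effect | 0 | 6.7 |
| 3% placebo risk, 70% reduction (0.03 × 0.70) | 2.1 | 7.2 |
| Same risk difference as non-Omicron | 8.4 | 8.4 |

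The risk difference generally changes even with equal relative efficacy, because it also depends on the Omicron placebo risk. The documents give neither an Omicron event rate nor an Omicron effect, so every d is an assumption and no power change is stated. SAP Section 1 does not expect adequate efficacy against Omicron, which points towards the low end of the range.

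**The case against.** The strongest reply is that this is a stale table column. For 1a, 2 and 3, mFAS-non-Omicron appears in the set definition, the hypothesis section, the key secondary section, the subgroup section, the per-protocol definition and the protocol. The Section 7 statement of no changes from the protocol also rules out a FAS primary analysis. That stands: no confirmatory test, alpha or power statement is left undefined.

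Estimand 1b is supplementary and outside the testing hierarchy. SAP Section 1 makes Omicron efficacy exploratory, and Appendix H gives 1b the same target population as 1a, so its intended set can be inferred. It can, but only by inference against the one set actually printed. The statement in 5.5.2 that the final model matches the primary analysis fixes the model, not the population.

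Sharing a set may also not make the 1a and 1b comparison clean. The primary analysis counts missing status as no event, whereas 5.5.2 can be read as multiply imputing all missing outcomes. That is a fair limit on what the correction achieves, but it is no reason to let the populations differ too.

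The figures rest on an Omicron risk difference the documents do not supply, and they use the inputs of 1a rather than 1b. They are illustrative: they show that the two sets target different quantities, not that a planned result is at risk. Finally, the silence of Appendix H on variant is an omission, not a statement that Omicron participants belong in the target population.

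**Conclusion.** The concern holds and should be fixed before unblinding. Appendix I states an analysis-set rule that gives the wrong population if followed. For 1a, 2 and 3 it contradicts clear body text, and the need is to remove the contradiction. For 1b it is the only set printed, so following the plan as written would bring Omicron participants into a supplementary analysis of the primary endpoint.

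The difference in population, about 79 of 399, follows from the SAP's own counts, of which the 320 is approximate. The shift in risk difference, from 8.4 points to between 6.7 and 8.4 in the cases shown, rests on the planning inputs, an equal split by arm and an assumed Omicron effect.

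**What to change.** Before unblinding:

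1. In SAP Appendix I, replace FAS with mFAS-non-Omicron in the Analysis Set column for Estimands 1a, 1b, 2 and 3.
2. In SAP 5.5.2, state that Estimand 1b is estimated in the mFAS-non-Omicron analysis set.
3. In SAP Appendix H, restrict the Estimand 1a target population to participants infected with a non-Omicron variant of SARS-CoV-2. The other estimands inherit it.
4. In SAP Appendix I, change the delta-method reference from Appendix K (criteria for potentially clinically significant events) to Appendix J, where the algorithm is given.

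While doing this, the reference to Appendix H in SAP 5.5.3 could be corrected too, since the overview of estimation and sensitivity analyses it describes is in Appendix I. All of this is SAP wording, and no analysis is added.
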